5.3 Other Outcomes of Interest

Retrospectively data will be analyzed to identify the possibility of treatment selection (mature graft vs. immature graft) in relation to the time after onset of symptoms (acute vs chronic cartilage lesions) in order to determine if one treatment is more beneficial than the other (e.g. higher stability, better integration etc.).

In addition a subgroup analysis to compare the outcome with regard to the localization of the defect (patella vs. femoral condyle/trochlea) will be performed after the study.

5.4 Safety Outcomes

The study will evaluate the safety of the implantation of an immature or a mature graft by the number of SADRs or SUSARs from baseline assessment up to 60-months follow-up assessment.

Adverse events/adverse drug reaction will be graded according to severity, expectedness, and relationship to trial treatment and reported according to the regulations.

No adverse events are expected except for those associated with any operation (see chapter 3.7)

Document:	Clinical Study Protocol
Version:	V07
Page number:	49 of 80
Acronym	Nose to Knee II

6. STUDY DESIGN

6.1 General study design and justification of design

This study is an interventional phase II study comparing the efficacy of a mature graft vs. an immature graft in cartilage repair after traumatic injury. 108 patients will be enrolled in 5 clinical centers in order to determine the possible benefits and superiority of a mature graft as compared to an immature graft. Patients will be randomized to ensure equal numbers in each treatment group at each center, but there will be no blinding in this study due to the fact that the manufacturing processes for the two IMPs have a different duration. The implantation date, thus the time after biopsy harvesting required for manufacturing of the graft, will disclose to both patient and surgeons to which treatment group the patient was assigned.

After the initial screening procedures, including MRI and blood tests, the patient is asked to fill out the baseline questionnaires and a biopsy is taken from the nasal septum. Either about three or five weeks later, depending on the treatment group, the IMP is implanted in the cartilage defect in the knee. The follow-ups at week 6 include only clinical issues such as wound healing. After 3, 12 and 24 months patients are additionally assessed by MRI and given validated questionnaires (12 and 24 month) to self-assess their condition. Patients are enrolled in the trial for 2 years, but will be asked to volunteer for further assessment by questionnaires for up to 5 years (see study schedule in summary).

In addition to the follow-ups, the patients will receive continuous physiotherapy starting shortly after implantation and lasting up to 1 year post-operatively if necessary.

A potential limitation in this trial is the fact that surgeons and patients are aware which IMP is implanted in the defect due to the properties and appearance of the IMP (surgeons) and the time between biopsy and implantation date (patient). However, although the assessment for the primary outcome is subjectively performed by the patient using validated questionnaires, the secondary outcome is assessed by independent medical personnel.

6.2 Methods of minimizing bias

6.2.1 Randomization

A permuted-block (2, 4 and 6 size) randomisation method will be performed. This method will prevent confounding of the treatment effect with "disease duration". For each centre there will be a randomisation list. The list will be generate by Sealed Envelope online software application (https://www.sealedenvelope.com/) and provided to database manager in order to implement and allow the automatic group assignation.

6.2.2 Blinding procedures

The study will be unblinded. Manufacturing of immature grafts is performed in a shorter time than for the mature grafts and therefore the operation date is at an earlier time point, thus disclosing the type of IMP implanted. In addition the physical properties of the two IPMs are different in terms of handling and appearance and thus can be easily identified by the surgeons. Therefore, it is not feasible to blind the study.

6.2.3 Other methods of minimizing bias

Patients will fill out validated questionnaires, widely used in clinical assessment for the efficacy of cartilage repair treatment.

All MRIs of all clinical centers will be analyzed at the University Hospital Basel by medical personnel with special focus on cartilage MRI. They will be blinded to assess for MOCART and 3D MOCART scores and dGEMRIC evaluation.

6.3 Unblinding Procedures (Code break)

Not applicable

Document:	Clinical Study Protocol
Version:	V07
Page number:	50 of 80
Acronym	Nose to Knee II

7. STUDY POPULATION

Patients presenting at hospitals will be treated in five clinical centers (Switzerland, Germany, Italy and Croatia) by the respective PIs as mentioned in Chapter 1.2. Harvesting of the starting material (nasal cartilage biopsy and blood) will be performed as an outpatient procedure, while the implantation will be performed as an in-patient procedure in the respective hospital. At each clinical center a defined number of patients should be enrolled (half for therapy with an immature graft, half for therapy with a mature graft). In case that less patients are enrolled in one of the centers, another center would have the possibility to enroll more patients than initially planned.

7.1 Eligibility criteria

Participants fulfilling all of the following inclusion criteria are eligible for the study:

- Patient is □18 and □65 years old at time of screening.
- Patient has a localized articular cartilage defect of the femoral condyle and/or the trochlea and/or patella of the knee. 2 localized cartilage defects are accepted if the total defect size is □ 8 cm², both cartilage defects are located at the femoral condyle and/or the trochlea and/or patella and both cartilage defects are to be treated with N-CAM or N-TEC.
- Patient has a defect of grade 3 or 4 according to the ICRS classification.
- Patient has a defect size □2 and □8 cm² as assessed by MRI/arthroscopy.
- Patient has an opposite intact (□CRS Grade 2) articulating joint surface (no "kissing lesions").
- Patient has an intact meniscus (maximum 1/2-resection).
- Patient has a stable knee joint or sufficiently reconstructed ligaments. If not, ligament repair has to be done during the operation or within 6 weeks of the planned cartilage treatment.
- Patient has a maximum baseline score of 75/100 in the KOOS subjective knee evaluation.
- Patient is willing and able to give written informed consent to participate in the study and to comply with all study requirements, including attending all follow-up visits and assessments and to complete postoperative rehabilitation regimen.

The presence of any one of the following exclusion criteria will lead to exclusion of the participant:

- Patient is the investigator or any sub-investigator, research assistant, pharmacist, study
 coordinator, other staff or relative thereof directly involved in the conduct of the protocol or in a
 dependency or employment with the sponsor.
- Patient is unable to understand the patient information
- Patient is unable to undergo magnetic resonance imaging (MRI) or is sensitive to gadolinium
- Patient has had prior surgical treatment of the target knee within 12 months using
 mosaicplasty and/or microfracture (Note: prior diagnostic arthroscopy with debridement and
 lavage are acceptable within 12 months). Anterior cruciate ligament repair is accepted, if the
 target knee is stable or a primary ACL reconstruction is performed within 6 weeks of the
 planned cartilage treatment.
- Patient has free range of motion of the affected knee joint or □ 10° of extension and flexion loss.
- Patient has a relevant meniscus tear. Partial meniscal removal allowed, if not exceeding 1/2.
 Suture of meniscocapsular separation is allowed. Suture of meniscus tear is allowed if the
 same compartment is not afflicted by symptomatic cartilage injury, and the graft is planned for
 trochlea and /or patella and /or contralateral compartment. If the same compartment is
 afflicted, suture is not allowed in parallel, but if successful, cartilage treatment might be added
 12 months later.
- Patient has radiologically apparent degenerative joint disease in the target knee as determined by Kellgren and Lawrence grade >2.
- Patient has evidence of joint disease e.g. chronic inflammatory arthritis, and/or infectious arthritis.
- Patient has an unstable knee joint or insufficiently reconstructed ligaments. If ligament repair
 is necessary, the repair has to be performed during the operation or within 6 weeks of the
 planned cartilage treatment.
- Patient has malalignment (no valgus- or varus-deformity) in the target knee □ 5°. In suspected cases, the mechanical axis must be established radiographically through complete leg imaging during standing and in a.p. or rather p.a. projection. If alignment surgery is necessary, surgery has to be performed within 6 weeks of the planned cartilage treatment.

Document:	Clinical Study Protocol
Version:	V07
Page number:	51 of 80
Acronym	Nose to Knee II

- Patient has an osteochondral defect which cannot be reconstructed (bony substance defect of >3mm depth need to be reconstructed with autologous bone graft from tibia or iliac crest).
 Bone marrow edema is allowed.
- Any concomitant painful or disabling disease of the spine, hips, or lower limbs that would interfere with evaluation of the afflicted knee.
- Patient has a known systemic connective tissue disease.
- Patient has a known autoimmune disease.
- Patient has a known immunological suppressive disorder or is taking immunosuppressives.
- Patient is currently systemically or intra-articularly taking steroids and/or has used steroids within the 30 days prior to the planned treatment.
- The patient has a known history of HIV/AIDS. (Protection of staff)
- The patient has a known history of Treponema pallidum (syphilis). (Protection of staff)
- The patient has an active hepatitis B or C infection with verified antigens. Patients with a cured hepatitis B or C infection and/or verified antibodies are not excluded. (Protection of staff)
- The patient has at the site of surgery an active systemic or local microbial infection, eczematization or inflammable skin alterations (including Protozoonosis: Babesiosis, Trypanosomiasis (e.g. Chagas-Disease), Leishmaniasis, persistent bacterial infections, such as Brucellosis, spotted and typhus fever, other Rickettsiosis, Leprosy, Recurrent Fever, Melioidosis or Tularaemia).
- Patient has a known history of cancer.
- Patient has a known history of primary hyperparathyroidism, hyperthyroidism, reduced kidney function (GFR < 80 ml/min), or prior pathological fractures, independent of the genesis.
- Patient has any degenerative muscular, vascular or neurological condition that would interfere
 with evaluation of outcome measures including but not limited to Parkinson's disease,
 amyotrophic lateral sclerosis (ALS), or multiple sclerosis (MS).
- Patient has a body mass index (BMI) >35 kg/m².
- Patient is pregnant, lactating or anticipates becoming pregnant within 24 months after surgery.
- Patient is currently participating, or has participated in any other clinical study within 3 months
 prior to the screening visit.
- Patient has known current or recent history of illicit drug or alcohol abuse or dependence defined as the continued use of alcohol or drugs despite the development of social, legal or health problems.
- Patient has psychiatric or cognitive impairment that, in the opinion of the investigator, would interfere with the patient's ability to comply with the study requirements, e.g., Alzheimer's disease
- Patient has any other condition, which, in the opinion of the investigator, would make the patient unsuitable for the study.
- · Patient is unable to tolerate local anesthesia
- Any known allergies, especially for porcine collagen, penicillin or streptomycin
- Patient is unwilling and/or unable to give written informed consent to participate in the study and to comply with all study requirements, including attending all follow-up visits and assessments and to complete postoperative rehabilitation regimen.

Intraoperative Exclusion Criteria:

- Patient has a total defect size <2 or defect size extends graft size and could therefore not be treated in total.
- Patient has >2 independent cartilage lesions
- Patient has symptomatic full-thickness (ICRS Grade 3 or 4) of tibial plateau.

7.2 Recruitment and screening

There is no advertisement for recruitment, since no healthy volunteers are eligible for the trial. No compensation or payment will be given to the participants. Patients attending for normal consultation at the 5 clinical centers will be screened for participation. If diagnosed with one or two symptomatic, cartilage lesions on the femoral condyle and/or trochlea and/or patella, patients will be informed of the trial and asked to participate. Before enrollment in the study the patient will receive information in an oral and written manner by the PI of the respective center and will be given time to discuss the treatment options and study participation with relatives or close persons. Patients will not be coerced into participating and will not suffer any disadvantage in treatment by declining to participate: they will be treated according to current standards. On signing the informed consent, the patient will be

Document:	Clinical Study Protocol
Version:	V07
Page number:	52 of 80
Acronym	Nose to Knee II

investigated, to see if they are eligible for the clinical trial and meet the inclusion and exclusion criteria defined in the study protocol. A baseline MRI will be performed, the questionnaires filled out by the patient and screening for pregnancy, if applicable, as well as for viruses and other parameters listed in the exclusion criteria carried out. If the patient complies with the eligibility criteria, they will be assigned to a treatment group, noted in the enrolment log and given a Patient-ID.

7.3 Assignment to study groups

The study group is assigned in phase of patient acceptance to the trial by the MyClinical Data database. Once the investigator creates the patient schedule and confirm that the patient is eligible for the study, according to inclusion and exclusion criteria and following consent form signed by the patient, the software will attribute to study group based on random algorithm.

7.4 Criteria for withdrawal / discontinuation of participants

Patients can be excluded from the study by the respective PIs at any point for the following reasons:

- Medical reasons where a continuation of the trial would jeopardize the health of the patient
- Withdrawal of informed consent (final medical follow-up mandatory for patient safety)
- Non-compliance with the required procedures as stated in the patient information and informed consent or refusal of the follow-up examinations which are necessary to assess the safety and efficacy of the treatment
- Abortion of the clinical study
- Contamination of the IMP during manufacturing
- · IMP manufacturing not successful
- Patient fulfills intraoperative exclusion criteria (section 7.1)

In case patients are excluded from the study, the PI will inform the patient and discuss a final medical follow-up date with them. The treatment cannot be terminated, since the intervention is an implantation. In case patients are excluded before implantation due to manufacturing issues or intraoperative exclusion criteria the surgeon will decide for a suitable treatment. The patient will be marked as excluded/study aborted in the enrolment log signed by the PI.

Patients excluded from the study after implantation will not be replaced, since a drop-out rate of 10% has been included in the power-calculation.

Document:	Clinical Study Protocol
Version:	V07
Page number:	53 of 80
Acronym	Nose to Knee II

8. STUDY INTERVENTION

8.1 Identity of Investigational Products (treatment / medical device)

8.1.1 Experimental Intervention (treatment / medical device)

Name: N-TEC

Sources: GMP production unit at Fraunhofer Institute, Germany (QP: PD [name]) or

DBM clean room at University Hospital Basel, Switzerland (QP: PD [name]

[name])

Composition: Chondro-Gide® combined with autologous nasal chondrocytes and extracellular matrix

containing cartilage specific proteins produced by the cells during preculture

Appearance: glossy-white (cartilaginous)

Size: 30x40 mm

Dose: 50 million cells

Route: Implantation in the cartilage defect of the knee and fixation by sutures

No commercial product available on the market.

8.1.2 Secondary study arm (treatment / medical device)

Name: N-CAM

Sources: GMP production unit at Fraunhofer Institute, Germany (QP: PD [name]) or

DBM clean room at University Hospital Basel, Switzerland (QP: PD [name]

[name])

Composition: Chondro-Gide® combined with autologous nasal chondrocytes and minimal to no

extracellular matrix deposited

Appearance: comparable to appearance of the Chondro-Gide® membrane alone

Size: 30x40 mm

Dose: 50 million cells

Route: Implantation in the cartilage defect of the knee and fixation by sutures

The commercial product comparable to the IMP is MACI[®]. This is also based on a matrix of porcine collagen Type I/III combined with autologous cells such as Chondro-Gide[®]. The difference is that for MACI[®], articular chondrocytes are used, while here nasal chondrocytes will be seeded in order to eliminate differences related to the cell source.

8.1.3 Packaging, Labelling and Supply (re-supply)

Labels for both products will be designed in accordance with the EU-GMP-guidelines, Volume 4 Annex 13. The labels will be in the local language of the country where the IMP will be used. The IMPs will be packed individually for each patient in a primary container (tube) within a secondary transport container and shipped by overnight courier to the respective clinic.

8.1.4 Storage Conditions

The product will be used immediately on receipt for implantation. Therefore no storage is intended.

Document:	Clinical Study Protocol
Version:	V07
Page number:	54 of 80
Acronym	Nose to Knee II

8.2 Administration of experimental and control interventions

8.2.1 Experimental Intervention

After manufacturing, the engineered tissue will be sent to the respective clinic, cut and shaped according to the defect size by the surgeon and immediately implanted using sutures for fixation until the graft heals in. The sutures are bioresorbable and dissolve with time. No additional preparations are necessary. Any unused part of the generated graft will be sent to the research lab (Tissue Engineering) in Basel involved in the clinical trial for research provided the patient has given prior consent.

8.2.2 Control Intervention

After manufacturing, the cell-seeded graft will be sent to the respective clinic, cut and shaped according to the defect by the surgeon and immediately implanted using sutures for fixation until the graft heals in. The sutures are bioresorbable and dissolve with time. No additional preparations are necessary. Any unused part of the generated graft will be sent to the research lab (Tissue Engineering) in Basel involved in the clinical trial for research provided the patient has given prior consent.

8.3 Dose / Device modifications

Not applicable.

8.4 Compliance with study intervention

Since the treatment itself (implantation) will be done by the surgeons and is a one-time application there is no risk of non-compliance. Surgical procedures will be harmonized by training and written SOPs.

In case of missed follow-up appointments, the surgeons will contact the patients and reschedule the visit. Questionnaires will be filled in by the patient directly at the time of follow-up using an eCRF. Adherence to recommendations regarding sport activities cannot be monitored; performance at physiotherapy will be asked of the patient, but not monitored.

8.5 Data Collection and Follow-up for withdrawn participants

Data will be collected until the time of withdrawal using the questionnaires and MRIs at the time of follow-up. No data will be collected afterwards. A final medical visit is recommended for the safety of the patient after withdrawal (minimum 1 year after treatment).

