The goal of this phase II clinical study is to compare the efficacy of a mature graft (with cartilage specific proteins) with the one of an immature graft (little to no cartilage specific proteins). In order to achieve this we will enroll 108 patients in the study and divide them in two groups, one receiving the immature graft and the other the mature graft. Patients must display a symptomatic, isolated cartilage lesion grade III-IV (according to the grading by the International Cartilage Repair Society (ICRS)) from 2 to 8 cm² on the femoral condyle and/or the trochlea and/or patella, have to be between 18-65 years old and must consent in oral and written manner in order to be enrolled in the study. After written informed consent has been obtained, the patients will be tested to see if they comply with all other inclusion and exclusion criteria. Subsequently blood (72ml) and a cartilage biopsy (tissue sample) from the nasal septum of the patient will be taken. The cartilage cells (Chondrocytes) are isolated from the tissue, expanded for 2 weeks and placed on a collagen matrix. For the immature graft the resulting construct will be cultured for 2 more days to allow the cells to adhere to the matrix. For the mature graft the construct will be cultured for 2 more weeks, to allow the cells to form cartilage tissue. After performing the quality tests the implant will be released by the manufacturer based on the sterility, cell viability and in case of the mature graft the deposition of matrix. Subsequently, the construct will be implanted in the knee. At 6 weeks as well as 3, 12 and 24 months after the operation follow-ups will be performed. During the follow-ups at 12 and 24 months questionnaires (KOOS, EQ-5d) will be filled out by the patient and MRIs will be performed at 3,12 and 24 months.

While the questionnaires (especially the Knee injury and Osteoarthritis Outcome Score TKOOS-Score)) provide subjective information about the efficacy of the treatment, the MRIs will shed light on the integration of the implant in the defect and give information about the quality of the repair tissue. Retrospectively the data will be analyzed in correlation to the status of the defect at time of treatment: acute (symptoms since less than 2 years) or chronic (symptoms since more than 2 years). This will give an indication whether one treatment (immature or mature graft) is more effective for a defined indication (acute or chronic) than the other.

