11.2 Determination of Sample Size

Sample size was estimated to be such that it would be able to show the superiority of N-TEC to N-CAM regarding the primary endpoint. Assumptions for sample size calculation were based on a study (Saris et al., 2008), in which an increase in a mean overall KOOS score after 18 months of 18 points to a final value of 74.73 with a standard deviation of 17.01 was reported. We have assumed that the effect size after 24 months will be at least as big.

Sample size was calculated using a resampling method. Each sample size ($n_i=1,...,21=40,...,160$) was evaluated by sampling R = 999 times, $n_i/2$ KOOS scores from a normal distribution with $\square=75$ and $\square=17$ for the N-CAM group, and $n_i/2$ KOOS scores from a normal distribution with $\square=75+\square$ and $\square=17$ for the N-TEC group. The size of \square was varied between 5 and 15. Values that exceeded 100 were set to 100.

N-CAM and N-TEC were tested for a difference in KOOS score using a two-sided t-test. Superiority of N-TEC to N-CAM was declared when the test showed a significant result. Sample size was set to ensure at least 80 % power (1 - \square = 0.8), at a significance level of \square = 5 %.

For this study, 108 patients should be recruited to ensure 97 evaluable patients at a power of 80%, considering an overall drop-out rate of 10% (Figure 11.2.1).

[figure not shown]

Fig. 11.2.1: Sensitivity of the sample size with regard to absolute difference in KOOS after 24 months (N-TEC vs. N-CAM), assuming a mean KOOS of 75 for N-CAM. An example is given based on an expected absolute difference of 10 score points (Curves are smoothed and are for illustrative purpose only)

Document:	Clinical Study Protocol
Version:	V07
Page number:	63 of 80
Acronym	Nose to Knee II

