11.4 Planned Analyses

11.4.1 Datasets to be analysed, analysis populations

The **full analysis set (FAS)** consists of all patients who were randomized, regardless of treatment conclusion or loss of follow-up (Intention To Treat principle – ITT).

The **per protocol set (PPS)** consists of all patients who have at least one follow-up measure. Patients in the PPS will be analyzed according to the treatment received without randomization.

The FAS will be used for the primary analysis and the secondary analyses as described. The PPS will be used for sensitivity analyses of the primary analysis and the secondary analyses as described.

Demographics and relevant baseline variables will be summarized for the FAS. Categorical data will be presented as frequencies and percentages. For continuous variables, the lower and upper quartile, the median, the mean and the standard deviation will be presented.

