4.2. Confidence intervals and p-values

The statistical testing will be two-sided with a significance level of 5%. All tests will be accompanied by an effect measure (N-TEC vs N-CAM) with a 95% confidence interval (95% CI).

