4.3. Adherence and protocol deviations

Major protocol deviations are:

- Violation of inclusion or exclusion criteria
- no outcome assessment at 12 or 24 months postop, respectively.

These protocol deviations will be summarised by treatment group using absolute and relative frequencies.

Cross-overs to the other treatment arm are not possible in the setting of this study. Since the treatment itself (implantation) will be done by the surgeons and is a one-time application there is no risk of non-compliance. Surgical procedures will be harmonized by training and written SOPs. Violation of inclusion or exclusion criteria such as further lesions in the knee might become apparent only at the time of surgery, so after randomization. Patients will not be followed-up in that case. In case of missed follow-up appointments, the surgeons will contact the patients and reschedule the visit. Questionnaires will be filled in by the patient directly at the time of follow-up using an eCRF. Adherence to recommendations regarding sport activities cannot be monitored; performance at physiotherapy will be asked of the patient, but not monitored.

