7.1. Analysis set

Two randomized patients did not receive treatment and study outcome (KOOS score at 24 months after surgery) was not assessed in these patients. So conducting the analysis according to ITT was not possible. We hence analysed the PPS instead of the FAS.

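### KOOS collection stops when an investigator excludes a randomised patient, although the protocol's primary analysis set is everyone randomised; these losses could differ by arm

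*Protocol*

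**What the plan says.** Protocol 11.4.1 defines the full analysis set (FAS) as the set that "consists of all patients who were randomized, regardless of treatment conclusion or loss of follow-up" and assigns it to the primary analysis. SAP 4.4 also names it as the analysis population.

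Protocol 8.5 collects questionnaires and MRI only up to withdrawal, and then: "No data will be collected afterwards". Section 9.2.6 offers those who leave early clinical visits, not outcome assessments.

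Protocol 7.4 opens with "Patients can be excluded from the study by the respective PIs at any point for the following reasons". Withdrawn consent is one reason on its list. Others are medical reasons, non-compliance, contamination of the product, unsuccessful manufacture and intraoperative exclusion criteria. Randomisation is at visit 2, biopsy at visit 3 and implantation at visit 4 (Protocol 9.1, 9.3.2), so manufacturing and intraoperative exclusions always follow randomisation.

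SAP 4.3 covers eligibility violations that become apparent at surgery: "Patients will not be followed-up in that case".

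SAP 6.3.1 runs the primary analysis on the per-protocol set (PPS). SAP 7.1 explains that two randomised patients were not treated and had no 24-month KOOS, and concludes: "So conducting the analysis according to ITT was not possible".

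**The concern.** An all-randomised analysis needs an outcome, or at least an attempt to obtain one, from every randomised patient. Here the protocol itself stops collection for patients who may still be willing to complete a questionnaire. Patients excluded before implantation receive another treatment of the surgeon's choice (7.4), so their later KOOS is meaningful and belongs in a comparison by assigned arm.

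Such losses were foreseeable. Table 3.7.1 rates failure to generate a graft and contamination during media change as medium risks before mitigation.

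They could also be unequal. After seeding, N-TEC is cultured for two weeks and N-CAM for two days. The English study summary lists an extra release test "in case of the mature graft the deposition of matrix", and Table 3.1.1 lists longer production time as a drawback of N-TEC only. If more N-TEC than N-CAM patients drop out this way, and they differ in prognosis from those who stay, the arms are no longer comparable as randomised.

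**Working it through.** **The plan's own figure.** Inputs from Protocol 11.2: N-CAM mean 75, N-TEC mean 85 (the 10-point example), SD 17, scores above 100 set to 100, two-sided t-test at 5%, and "Sample size was set to ensure at least 80 % power". A simulation on these inputs (40,000 runs) gives about 80.2% to 80.5% power with 97 evaluable patients. Then 97 / 0.90 = 107.8, rounded up to 108. Both stated figures reproduce.

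**What the 10% allowance covers.** It covers power only. The same simulation, starting from 108:

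| Lost | Evaluable | Power |
|---|---|---|
| 0 | 108 | 84.6% |
| 2 patients | 106 | 83.7% |
| 10% | 97 | 80.5% |
| 15% | 92 | 78.1% |
| 20% | 86 | 75.6% |

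**Bias.** In one arm, let p be the fraction missing and g the observed mean minus the mean the missing would have had. The full-arm mean is (1 − p) × observed + p × (observed − g) = observed − p × g, so the observed mean is too high by p × g. For the difference N-TEC minus N-CAM with a common g:

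bias = (p in N-TEC − p in N-CAM) × g

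A shift in one arm is not enough. What counts against the 10-point threshold is the difference between arms. The documents give neither losses by arm nor g, so these are assumed ranges:

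| Loss N-TEC vs N-CAM | g = 10 | g = 20 |
|---|---|---|
| 2/54 vs 0 | 0.037 × 10 = 0.4 | 0.037 × 20 = 0.7 |
| 15% vs 5% | 0.10 × 10 = 1.0 | 0.10 × 20 = 2.0 |
| 20% vs 0% | 0.20 × 10 = 2.0 | 0.20 × 20 = 4.0 |
| 10% vs 10% | 0 | 0 |

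The first row places both known cases in one arm of 54. The other rows all average the planned 10%; 20% versus 0% is the extreme in which the whole allowance falls on one arm. The sign reverses if N-CAM loses more.

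**The case against.** The strongest reply has four parts.

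- **The two known cases prove little.** SAP 7.1 gives neither arm nor reason. A reader might infer that the exclusion rules removed these patients, or that they were lost because of their arm. The documents support neither; withdrawn consent before surgery fits equally well. This part stands.
- **Arm-dependence is not shown.** Biopsy and two-week expansion are the same in both arms, so biopsy contamination or a low cell count arises before the arms diverge. The intraoperative criteria are anatomical (defect size, number of lesions, tibial plateau) and both grafts measure 30 x 40 mm (8.1.1, 8.1.2), so bias there would need an unblinded surgeon's judgement to be affected. This stands in large part: the arm-specific route is mainly the longer culture and the matrix test, and it is a possibility.
- **Two missing values did not force the change of analysis set.** SAP 6.4 already plans multiple imputation with 20 data sets for a missing primary outcome, and Protocol 11.5 considers imputation for the FAS. A reader might infer that stopping follow-up made ITT impossible; dropping it was partly an analysis decision. Imputation is still a weaker substitute for data: never-implanted patients have no post-surgery values to inform it, and it would borrow from treated patients under a missing-at-random assumption.
- **Some follow-up continues.** Protocol 10.1.3 follows adverse events in withdrawn patients until resolved. That is true, but it does not supply KOOS. Non-compliance under 7.4 also includes refusing follow-up, where no outcome could be had anyway.

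**Conclusion.** The inconsistency is in the text and rests on no assumption: an all-randomised primary set is paired with a rule that ends outcome collection after exclusions other than withdrawn consent. SAP 4.3 is narrower than Protocol 8.5, since it covers only eligibility violations found at surgery.

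The likely bias from the two known cases is small: 0.4 to 0.7 points at most, if both were in one arm of 54 and the gap is 10 to 20 points. They are 2/108 = 1.9% of patients if 108 were randomised, which the SAP does not confirm. With a 15% versus 5% loss the bias would be 1 to 2 points, or 10% to 20% of the 10-point threshold. The gap and the split by arm are assumptions throughout.

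The documents do not show that exclusions differed by arm or that the result is biased. They do show that the plan left this open when it could have been prevented cheaply. It should be corrected, and the handling disclosed.

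**What to change.** 1. In Protocol 7.4 and 8.5, separate stopping or not receiving the implant from withdrawing consent.
2. For every randomised patient who still consents, including those never implanted, collect KOOS and EQ-5d at 12 and 24 months. The endpoint is timed from surgery, so state an anchor for the non-implanted: date of randomisation or planned surgery date.
3. The SAP is dated 28 November 2022 and the last follow-up was planned for 10/2021. Where the window has passed, make one dated contact attempt and flag late values. The voluntary questionnaire follow-up to 5 years may give an opportunity.
4. Replace the SAP 4.3 sentence with an accurate statement of how these patients were and will be handled. Simply deleting it would hide what was done.
5. Report post-randomisation exclusions by arm and reason, including for the two patients in SAP 7.1.
6. Report the all-randomised analysis with the SAP 6.4 imputation, plus a sensitivity analysis for outcomes not missing at random, beside the PPS result.
7. Reconcile Protocol 8.5 with 10.1.3 on adverse-event follow-up after withdrawal, and with 7.4, which makes the final medical follow-up mandatory after withdrawn consent where 8.5 only recommends a final visit.

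Cost: an amendment, which if substantial needs ethics and authority approval in four countries (Protocol 2.10), and electronic questionnaires for a few patients, with no added procedure. The required sample size stays at 108. Including untreated patients may slightly dilute the estimated effect, so the 84.6% power with all 108 observed is an upper bound.
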